- Group 1: SC ramucirumab 350 mg (1 injection of 2 mL×175 mg/mL)
- Group 2: SC ramucirumab 700 mg (2 injections of 2 mL×175 mg/mL)
- Group 3: IV ramucirumab to a maximum of 350 mg (60-minute IV infusion; maximum 35 mL×10 mg/mL)
- Group 4: SC ramucirumab 350 mg (2 injections of 2 mL×87.5 mg/mL)
- Group 5: SC ramucirumab 350 mg (2 injections of 1 mL×175 mg/mL)
- Optional Group 6: SC ramucirumab (maximum planned dose level, 350 mg, given as slow SC infusion).

Groups 4 and 5 are planned to investigate single SC ramucirumab dose of 350 mg with different volume of injection (2 injections of 1 mL×175 mg/mL) and different concentration of the drug product (2 injections of 2 mL×87.5 mg/mL) compared to the first group dosed at 350 mg (1 injection of 2 mL×175 mg/mL). Data from these groups will provide insight about the effect of injection volumes and ramucirumab concentration on the PK and tolerability of SC ramucirumab.

The initial dose planned for Groups 3 and 6 are to be modified based on emerging data discussed at the safety review between sponsor and investigator (see Section 4.3 for rationale).

More precisely, following the emerging data from Groups 1 and 2, the study doses are modified downwards. This is pending the full safety review of all data from Groups 1 and 2. The IV dose (Group 3) will not exceed 350 mg, and the subsequent SC doses will be capped at 350 mg (Groups 4 through 6). In Section 4.3 (Justification for Dose), Groups 1 and 2 safety data justifying that change are presented in more detail.

Disclosure Statement: This is a PK and safety study to test both the marketed ramucirumab IV formulation and a novel ramucirumab SC formulation in healthy participants with the objective of comparing PK exposure and safety following both routes of administration.

Number of Participants:

Approximately 60 participants will be enrolled and randomly assigned to study intervention to obtain at least 48 evaluable participants for an estimated total of at least 8 evaluable participants per intervention group (Section 9.2).

Intervention Groups and Duration:

Participants will be screened within 28 days prior to Day 1 of dosing for each group. Within each group, participants will be randomized to receive a single dose of IV or SC ramucirumab or placebo (7 ramucirumab:3 placebo per group).

The dosing groups or treatment intervention are as stated in the study design:

[figure not shown]
- Group 1: SC ramucirumab 350 mg (1 injection of 2 mL×175 mg/mL)

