4.1. Overall Design

This is a single-site study in healthy participants who will receive a single dose of SC or IV ramucirumab. The study will be participant- and investigator-blinded, randomized, and placebo-controlled (7 ramucirumab:3 placebo per group/dose level). Placebo will be used as a comparator for both IV and SC to allow interpretation of safety and tolerability data following administration.

There will be sentinel dosing in this protocol; the initial 2 participants will be randomized/dosed (1 ramucirumab:1 placebo), and subsequently (the next day), the remaining participants in the group will be dosed. This will be subject to a satisfactory safety review by the investigator. This will occur on the first dose of SC (Group 1).

In Section 4.2, additional rationale is presented for the selection of healthy participants for this investigation.

Participants will be screened within 28 days prior to Day 1 of dosing for each group. Participants will be admitted to the CRU as part of an inpatient visit on Day -1 and will be sequentially enrolled. In each group, participants will be randomized to receive a single dose of IV or SC ramucirumab or placebo (7 ramucirumab:3 placebo per group).

There will be at least a 2-week safety observation period between the titrating SC injection groups (Groups 1 and 2), and between the SC and IV groups (Groups 2 and 3) while local laboratory data is reviewed by the sponsor and investigator. If the safety review is acceptable, Groups 4 and 5 may be dosed simultaneously to Group 3, as no dose escalation is occurring in those groups. Group 6 may be dosed with an infusion pump once the sponsor has reviewed both the safety and PK data (Groups 1 through 3) if the safety results are acceptable and if there is scientific value for investigating an additional group. The dose for Group 6 will be determined (maximum dose 350 mg). The plan for periodic reviews is presented Section 9.5.

The dose levels are provided below and may be adjusted based on safety reviews for preceding groups.

The participants receiving ramucirumab in each group will be administered the following dose level (up to 3 dose levels predicted to be ultimately used for therapeutic intent [see Section 4.3 for dose rationale]):

- **Group 1 will test a ramucirumab 350-mg SC dose**
 - administered at a concentration of 175 mg/mL as 1×2-mL injection.
- **Group 2 will test a ramucirumab 700-mg SC dose**

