The top planned SC ramucirumab dose in Group 6 was initially planned as a maximum dose level of 1400 mg in a previous protocol version. Since then, Groups 1 and 2 (350 mg and 700 mg SC) have been enrolled and received study treatment, and 2-week postdose safety data from those groups were reviewed. Consequently, after the safety review, the maximum dose is to be capped at 350 mg as this dose was associated with an acceptable safety profile. This edict applies to all subsequent groups.

The emerging data suggests Group 6 may not be needed given the planned collection of information at the 350 mg SC dose (Groups 1, 4, and 5).

In addition to those SC ramucirumab dose levels, a single dose of up to 350-mg ramucirumab administered IV (via 60-minute infusion) is planned to enable determination of the absolute bioavailability following SC administration.

The initial ramucirumab SC doses will be determined from the safety data from previous clinical experience with IV ramucirumab, as it is understood that the IV administration leads to higher plasma levels and it is expected that tolerability will be better with the SC administration.

In summary, ramucirumab dose levels that are proposed for Study JVDT are:

- ramucirumab IV, originally 700 mg dose level and subsequently modified to 350 mg IV following safety review of Groups 1 and 2
- ramucirumab 350 mg SC
- ramucirumab 700 mg SC

The table below presents the margin of safety (based on C_{max} or AUC) relative to the toxicology monkey study. The table uses the originally planned maximum ramucirumab dose IV and SC, in the absence of any ramucirumab data in healthy participants and based on the assumption that ramucirumab IV PK properties are similar in healthy participants and in patients and the assumption for bioavailability following SC as stated above.

Predicted Margin of Safety at Maximum Dose in Study JVDT

Study	Dose (mg/kg) and Route of Administration	C _{max} (µg/mL)	Margin of Safety	AUC ₀₋₁₆₈ (mg.h/mL)	Margin of Safety
SNBL 023.04 (5-week monkey)	40 (IV) ^a NOAEL	1460	-	189	-
JVDT (SAD in healthy participants)	10 (IV) ^b	211	7X	18.6	10X
	20 (SC) ^c	139	11X	15.3	12X

Abbreviations: AUC₀₋₁₆₈ = area under the curve during the dosing interval; C_{max} = maximum observed

concentration; IV = intravenous; PK = pharmacokinetics; popPK = population pharmacokinetics; SAD = single ascending dose; SC = subcutaneous.

a 40 mg/kg was the no-adverse-effect level in this study.

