b 700 mg is equivalent to 10 mg/kg in a 70-kg human. Exposure values from RELAY popPK model report the mean, as the toxicology data report the mean, which is consistent with the median values reported in [Appendix 6](#).

c 1400 mg is equivalent to 20 mg/kg in a 70-kg human. The human PK model simulation of SC regimen indicates a mean C_{max} of 139 µg/mL and mean AUC over the first week AUC₀₋₁₆₈ of 15.3 mg.h/mL following a ramucirumab 1400-mg SC administration. [Appendix 6](#) reports median value (very close to these mean values).

A NOAEL of 40 mg/kg was established in a 5-week repeat dose study in monkey. At this dose, C_{max} and AUC values are 11-fold and 12-fold higher than the anticipated systemic exposure following a single SC dose of 1400 mg in Study JVDT. At this dose, C_{max} and AUC values are 7-fold and 10-fold higher than the anticipated systemic exposure following a single IV dose of 700 mg in Study JVDT.

Therefore, nonclinical data provides support for the safety of the IV and SC dose of ramucirumab to be investigated in normal, healthy human participants (Section [10.6](#)).

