9.5. Interim Analyses

No interim analyses are planned for this study. If an unplanned interim analysis is deemed necessary for reasons other than a safety concern, the protocol must be amended.

However, there will be periodic reviews of data to assess safety, tolerability, and PK data. There will be sentinel dosing in this protocol; the initial 2 participants will be randomized/dosed (1 ramucirumab:1 placebo), and subsequently (the next day), the remaining participants in the group will be dosed. The following information belongs in this section:

- Safety reviews are planned prior to dose escalation after 2-week safety data are available.
- PK data may be reviewed for Groups 1 and 2 if timing permits.
- PK data will be reviewed once Group 1 through 3 PK samples have been collected (cutoff 2-week sample collection in Group 3).

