10.6. Appendix 6: Pharmacokinetic Profile Simulation (Intravenous versus Subcutaneous)

The PK profile for IV (10 mg/kg Q2W) and SC administration of ramucirumab (Left panel: 1400-mg SC loading dose on Day 1 followed by QW SC 700 mg; Right panel: 1400-mg SC loading dose on Day 1 followed by twice-weekly [BIW] SC 350 mg) is shown in the figure below.

Abbreviations: BIW = twice weekly; IV = intravenous; LD = loading dose; Q2W = every 2 weeks; QW = once weekly; Ram = ramucirumab; SC = subcutaneous.

**Model-Simulated Ramucirumab AUC, Average, Trough, and Peak Concentrations
Following Intravenous (10 mg/kg Q2W) and Subcutaneous Administration of
Ramucirumab (1400-mg SC loading dose on Day 1 followed by either weekly [QW] SC
700 mg or twice weekly [BIW] SC 350 mg)**

	10 mg/kg Q2W IV RELAY		SC LD 1400 mg + SC MD 350 mg BIW		SC LD 1400 mg + SC MD 700 mg QW		RATIO	RATIO
	Median	5 th -95 th percentile	Median	5 th -95 th percentile	Median	5 th -95 th percentile	SC 350 / IV 10	SC 700 / IV 10
Week 1&2 PK parameters								
AUC1 mg.h/mL	18.1	13.2-25.4	16.3	10.6-25.1	14.8	9.61-22.9	0.90	0.82
AUC2 mg.h/mL	26.2	18.2-38.2	39.2	24.8-61.5	35.8	22.6-56.2	1.50	1.37
C _{av} µg/mL Week1	108	79-151	97	63-149	88.1	57-136	0.9	0.82
C _{av} µg/mL Week2	48	30-76	136	85-217	125	77-198	2.83	2.59
C _{max} µg/mL	206	153-285	141	87-227	134	83-212	0.68	0.65
C _{trough} µg/mL	35	16-58	133	80-218	112	66-184	3.86	3.25
Steady state SS PK parameters								
AUC _{ss} mg.h/mL	48.0	30-75	59	33-102	59	34-102	1.23	1.23
C _{av} µg/mL	143	90-223	176	99.4-305	176	100-305	1.23	1.23
C _{max} µg/mL	285	200-412	178	100-308	186	106-318	0.62	0.65
C _{trough} µg/mL	77	38-138	170	96-296	157	86-278	2.21	2.04
Ratio C _{trough} SS/WEEK1&2	2.23		1.28		1.40			
C _{average} to trough WEEK2	1.38		1.02		1.12			
Peak to trough at SS	3.7		1.05		1.18			

Abbreviations: AUC_{ss} = area under the curve at steady state over 2 weeks; AUC1 = area under the curve during the first week of treatment; AUC2 = area under the curve during the first 2 weeks of treatment; BIW = twice weekly; C_{av} = average concentration; C_{max} = maximum concentration; C_{trough} = trough min concentration at the end of the dosing interval; IV = intravenous; LD = loading dose; MD = maintenance dose; PK = pharmacokinetic; SC = subcutaneous; SS = steady state; Q2W = every 2 weeks; QW = once weekly.

**Model-Simulated Ramucirumab AUC, Average, Trough, and Peak Concentrations

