### **10. INTERIM ANALYSES**

No interim analyses are planned for this study. If an unplanned interim analysis is deemed necessary for reasons other than a safety concern, the protocol must be amended.

However, there will be periodic reviews of data to assess safety, tolerability, and PK data. There will be sentinel dosing in this protocol, the initial 2 participants will be randomized/dosed (1 ramucirumab:1 placebo), and subsequently (the next day), the remaining participants in the group will be dosed. The following information belongs in this section:

- Safety reviews are planned prior to dose escalation after 2-week safety data are available.
- The Lilly PK team will review the PK data for Groups 1 and 2 if timing permits.
- The Lilly PK team will review the PK data once Group 1 through 3 PK samples have been collected (cutoff 2-week sample collection in Group 3).

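### The 350 mg cap on IV Group 3 rests on SC tolerability at that dose; predicted IV Cmax exceeds that of the rejected 700 mg SC dose, and no PK comparison is required before IV dosing

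*Protocol*

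**What the plan says.** Section 4.3 of the protocol reports that Groups 1 and 2 (350 and 700 mg SC) had been dosed and their 2-week safety data reviewed. It concludes that "the maximum dose is to be capped at 350 mg as this dose was associated with an acceptable safety profile", and extends this to all subsequent groups. The Amendment (c) rationale states that 700 mg was judged unacceptable because of asymptomatic transaminase increases. The synopsis (1.1) qualifies the downward change: "This is pending the full safety review of all data from Groups 1 and 2". Section 4.1 allows doses lower than 350 mg.

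On exposure by route, 4.3 says "it is understood that the IV administration leads to higher plasma levels". Its margin-of-safety table still uses the originally planned 700 mg IV and 1400 mg SC doses and compares them with monkeys, not with each other.

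On PK before IV dosing, protocol 9.5 says "PK data may be reviewed for Groups 1 and 2 if timing permits" and SAP section 10 says "The Lilly PK team will review the PK data for Groups 1 and 2 if timing permits". The PK review that must happen comes after the 2-week samples from Group 3. Under 4.1, the step from Group 2 to Group 3 needs a safety observation period of at least 2 weeks with laboratory review. Optional Group 6 (SC, at most 350 mg) must wait for PK from Groups 1 to 3.

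**The concern.** A milligram amount tolerated by one route is carried to another route that the protocol expects to give higher concentrations. The purpose of the cut was to keep healthy volunteers away from the exposure at which transaminases rose. Whether 350 mg IV does so depends on the exposure metric, and the plan neither makes that comparison nor requires one from the Group 1 and 2 samples. Sentinel dosing applies only to Group 1, so the first IV dosing in healthy participants has none.

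**Working it through.** **Inputs.** From the 4.3 table: 700 mg IV, mean Cmax 211 µg/mL and AUC(0-168) 18.6 mg·h/mL; 1400 mg SC, 139 and 15.3; monkey NOAEL, 1460 and 189. From the 4.3 text: F = 0.6 (90% prediction interval 0.44 to 0.79) and ka = 0.3/day, described as worst-case. From 2.1: half-lives of about 20 h and 10 to 14 days.

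**The plan's own figures reproduce.** 1460/211 = 6.9 (7X); 189/18.6 = 10.2 (10X); 1460/139 = 10.5 (11X); 189/15.3 = 12.4 (12X).

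**Scaling to the doses at issue** (dose-linear, patient IV PK, as 4.3 assumes):

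- 350 mg IV: 211/2 = 105.5; 18.6/2 = 9.30
- 700 mg SC: 139/2 = 69.5; 15.3/2 = 7.65
- 350 mg SC: 139/4 = 34.75; 15.3/4 = 3.825

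| Ratio at F = 0.6 | Cmax | AUC(0-168) | Total AUC |
|---|---|---|---|
| 350 IV / 700 SC | 105.5/69.5 = 1.52 | 9.30/7.65 = 1.22 | 350/(0.6 × 700) = 0.83 |
| 350 IV / 350 SC | 105.5/34.75 = 3.04 | 9.30/3.825 = 2.43 | 1/0.6 = 1.67 |

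**Sensitivity to F, 350 IV / 700 SC** (each ratio × 0.6/F). At F = 0.44: Cmax 2.07, AUC(0-168) 1.66, total 1.14. At F = 0.79: 1.15, 0.92, 0.63. The excess disappears above F = 0.6 × 1.52 = 0.91 for Cmax, 0.6 × 1.22 = 0.73 for AUC(0-168), and 0.50 for total AUC.

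**Is 139 µg/mL a single-dose Cmax?** Footnote c to the table reads "The human PK model simulation of SC regimen indicates a mean" Cmax of 139 and says the Appendix 6 medians are very close. Appendix 6 simulates regimens such as "1400-mg SC loading dose on Day 1 followed by QW SC 700 mg". Its Week 1 and 2 Cmax differs between two regimens with the same loading dose (141 with 350 mg twice weekly, 134 with 700 mg weekly), so it includes maintenance doses. The first-week AUC of the weekly arm (median 14.8, against the table mean of 15.3) should already be a single-dose value, taking the first maintenance dose to fall on Day 8.

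**Reconstruction (an assumption, not a document figure).** I used a two-compartment model with first-order absorption. The IV part was set either to 211 and 18.6 with the documented half-lives, or to the Appendix 6 IV medians (206, 18.1, 26.2, trough 35). The second fit has a terminal half-life of 8.1 days, outside the range in 2.1.

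- At ka = 0.3/day and F = 0.6, a single 1400 mg SC dose peaks at about 102 to 104 µg/mL. Adding 700 mg on Day 8 gives about 127 to 140, in line with the printed figures. The IV350/SC700 Cmax ratio is 2.01 to 2.05.
- These models give a first-week AUC of 14.2 to 14.4, below the printed 14.8 to 15.3, so their first-week AUC ratio (1.27 to 1.30) is too high and the printed 1.22 should stand. Raising ka to about 0.33 to 0.35/day matches the printed AUC and lowers the Cmax ratio to about 1.95.
- With F raised, the Cmax ratio is about 1.7 at F = 0.7 (1.95 × 0.6/0.7 = 1.67) and about 1.5 at F = 0.79 (1.95 × 0.6/0.79 = 1.48). With ka = 0.5/day and F = 0.7 it is also about 1.5.
- The two-week AUC ratio at F = 0.6 is 0.96 to 1.01.
- With faster absorption at F = 0.6, the first-week AUC ratio is 1.05 to 1.07 at ka = 0.5/day and about 0.95 at 0.8/day.

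**The case against.** The strongest reply is that only Cmax gives a sturdy excess. F = 0.6 and ka = 0.3/day are the protocol's worst-case values, chosen at the low end for SC absorption, and both inflate the IV/SC ratio. The first-week AUC excess vanishes with modestly better absorption. The signal came from 2-week data, and over two weeks the AUCs are about equal; total AUC favours IV. All of this stands, and it is why the point rests mainly on Cmax.

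Second, 350 mg is a ceiling. Lower doses are allowed, the liver exclusions were tightened, halting rules apply (6.6), participants stay in the unit to Day 8, and the minimum weight of 70 kg keeps 350 mg at or below 5 mg/kg. The monkey margins become about 14X (1460/105.5) and 20X (189/9.30), and 350 mg IV gives half the exposure of the patient 10 mg/kg IV dose. These are real safeguards, but none compares exposure with Group 2 before IV dosing. Patient experience does not settle the matter either: 700 mg SC was predicted at 0.33 of that patient Cmax (69.5/211; about 0.25 by reconstruction) and 0.41 of first-week AUC (7.65/18.6), and was still rejected. Section 4.2 adds that similar clearance in healthy participants and patients is not known.

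Third, the contrast with Group 6 carries little weight, because its PK condition dates from a planned 1400 mg dose.

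A reader might infer that 350 mg IV is more hepatotoxic than 700 mg SC. The documents do not support that: nothing in them ties the transaminase increases to Cmax rather than to early or total AUC.

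**Conclusion.** The point holds as a gap in the dose rationale and in the conditions for IV dosing. On the protocol's own assumptions, 350 mg IV is predicted above the rejected 700 mg SC on Cmax, by 1.52-fold as printed and about 1.9 to 2.0-fold if the printed SC Cmax includes maintenance doses. First-week AUC is 1.22-fold, only while F is below about 0.73 and absorption is slow. Two-week AUC is about equal (0.96 to 1.01) and total AUC is lower (0.83). Against the tolerated 350 mg SC, IV is higher on all three tabulated metrics at F = 0.6.

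This rests on dose-linear PK and on patient IV PK holding in healthy participants; the upper Cmax figures and the two-week figure also rest on the reconstruction. It shows neither that 350 mg IV is unsafe nor what lower dose would be right. The uncertainty is a reason to look at the measured concentrations first.

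**What to change.** In protocol 9.5 and SAP section 10, replace the optional review of Group 1 and 2 PK with a required one, and add the same condition to the Group 2 to Group 3 step in 4.1. Suggested wording:

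> Group 3 will not be dosed until the sponsor PK team has reviewed Group 1 and 2 concentrations through Day 15. The IV dose (350 mg or lower) will be set after comparing its predicted Cmax, AUC(0-168), two-week AUC and total AUC with Group 2 observations. The rationale, including acceptance of any predicted excess, will be kept in the dose-decision record.

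Total AUC for Group 2 will be partly extrapolated at that point. Do not fix a milligram ceiling in advance: the IV dose matching 700 mg SC on Cmax is 350/1.52, about 230 mg, from the printed table, but 350/1.95, about 180 mg, from the reconstruction. Concentrations stay with the sponsor PK team (protocol 8.5), so the site blind is kept.

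The cost is one protocol and SAP text change with ethics approval, plus assay turnaround, which the documents do not give. No samples or visits are added. Keeping the rationale in the decision record avoids a further amendment. Groups 4 and 5 need not wait; optional Group 6 would. If the IV dose is lowered, the same-dose comparison with Groups 1, 4 and 5 is lost.

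Separately, SAP 9.3.1 defines F as AUC[SC]/AUC[IV] × 100 with no dose term. For 700 mg SC against 350 mg IV this doubles the answer: a true 60% would be reported as 120%. For every SC group use F = 100 × (AUC[SC]/dose SC)/(AUC[IV]/dose IV).

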4.4. End of Study Definition

A participant is considered to have completed the study if he/she has completed the first 40 days of study procedures as per the schedule of events. If a participant does not complete the 40 days procedure, he/she maybe replaced.

The end of the study is defined as the date of the last visit of the last participant in the study or last scheduled procedure shown in the Schedule of Activities (SoA) for the last participant in the trial globally.

5. Study Population

Prospective approval of protocol deviations to recruitment and enrollment criteria, also known as protocol waivers or exemptions, is not permitted.

5.1. Inclusion Criteria

Participants are eligible to be included in the study only if all of the following criteria apply:

Age

1. Participant must be between the ages of 18 and 60 years of age, inclusive, at the time of signing the informed consent.

Type of Participant and Disease Characteristics

2. Participants who are overtly healthy as determined by medical evaluation including medical history, physical examination, vital sign measurements, including electrocardiogram (ECG), and laboratory tests
3. Have clinical laboratory test results within normal reference range for the population or investigative site, or results with acceptable deviations that are judged to be not clinically significant by the investigator; have a urinary protein value <2+ on dipstick urinalysis
4. Have venous access sufficient to allow for blood sampling and/or administration of study intervention for IV administration as per the protocol
5. Are reliable and willing to make themselves available for the duration of the study and are willing to follow study procedures

Weight

6. Body weight within ≥ 70 kg and body mass index (BMI) within the range of 18 to 32 kg/m^2 (inclusive)

Sex

7. Male and/or female

Contraceptive use by men or women should be consistent with local regulations regarding the methods of contraception for those participating in clinical studies.

a) Male participants:

- regardless of their fertility status, with a partner of childbearing potential, must for the duration of the study or for 5 months following completion of study drug administration, whichever is longer, agree to either:
 - remain abstinent, if this is their preferred and usual lifestyle (periodic abstinence [for example, calendar, ovulation, symptothermal, postovulation methods], declaration of abstinence just for the duration of a trial, and withdrawal are not acceptable methods of contraception), **or**

- use condoms, **and** ensure the partner uses
 - one highly effective (<1% failure rate) method of contraception, such as combination oral contraceptives, implanted contraceptives, or intrauterine devices, **or**
 - one effective method of contraception, such as diaphragms with spermicide or cervical sponges with spermicide
- with pregnant partners should use condoms during intercourse for the duration of the study or for 5 months following completion of study drug administration, whichever is longer
- who are in exclusively same-sex relationships (as their preferred and usual lifestyle) or with female partners of nonchildbearing potential are not required to use contraception
- should refrain from sperm donation for the duration of the study or for 5 months following completion of study drug administration, whichever is longer.

b) Female participants:

- will not be breastfeeding or planning to breastfeed during the study
- must have a negative pregnancy test at the time of screening
- must be of nonchildbearing potential defined as:
 - infertile due to surgical sterilization (bilateral oophorectomy, tubal ligation, or hysterectomy) or having a congenital anomaly (mullerian agenesis), **or**
 - postmenopausal, as evidenced by spontaneous amenorrhea for at least 12 months, **or**
 - a woman ≥ 55 years of age who is not on hormone therapy and who has had at least 12 months of spontaneous amenorrhea, or with a diagnosis of menopause prior to starting hormone replacement therapy

Informed Consent

8. Capable of giving signed informed consent as described in [Appendix 1](#), which includes compliance with the requirements and restrictions listed in the informed consent form (ICF) and in this protocol

